12. STATISTICAL ANALYSIS

- *Describe how your data will be used to test the hypotheses.*
- *State clearly what variables will be tested and what statistical tests will be used.*
- *Include sample size calculations.*
- *If this is a pilot study, state which variables will be examined for hypothesis generation in later studies.*

Patients with less than 7 days of CGM measurements will be excluded from analysis. Arithmetic mean glucose (AMG) will be calculated for each patient from

all CGM glucose measurements. A simple linear regression model will be applied to estimate the relationship between AMG and HbA1c. Once the relationship is established through the model, prediction of mean AMG together with 95% confidence intervals will be calculated at different levels of HbA1c. Influence of factors such as age, gender on the relationship between HbA1c and AMG will be examined through a multivariate regression model. Slopes and intercepts of the regression equations for the individual subgroups will be compared to those of the simple linear regression model. A quadratic regression model will also be applied if the relationship between the two variables is not linear. The same analysis will be performed to establish the relationship between AMG and serum fructosamine. Linear and quadratic regression models will be applied to estimate the relationship between AMG and HbA1c and serum fructosamine. If a linear relationship is established then slope, Y-intercept and correlation coefficient will be calculated. Mean AMG at different levels of HbA1c and serum fructosamine will be calculated. Glucose variability will be calculated as MAGE scores. First all the local maximum/minimum values are determined. The next step is an assessment of maximum/minimum pairs against the standard deviation (SD). If the difference from minimum to maximum is greater than the SD, this variation from mean measure is retained. If the local maximum/minimum is less than 1 SD it is excluded from further calculations. These troughs are retained and summed to achieve the MAGE score.

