Diabetes control is often assessed by tests of glucose levels over time, such as the glycosylated hemoglobin A1c (HbA1c) and fructosamine. In the later stages of chronic kidney disease (CKD) there is limited data available on the utility of these tests. There are reasons to believe that the tests may be less accurate in this population. Continuous glucose monitoring (CGM) offers an effective method for understanding the totality of glucose exposure and incidence of both hyperglycemic and hypoglycemic excursions. In the proposed study we plan to utilize CGM in patients with late stage CKD stages 3b-5 to 1) determine accuracy of HbA1c and serum fructosamine testing as measures of glucose control in patients with Type 2 Diabetes Mellitus (T2DM), 2) better understand test characteristics in the late stage CKD population (correlation, linear equation, slope, Y intercept, average glucose at different HbA1c levels), 3) develop a preliminary understanding of how test characteristics differ in late stage CKD compared to other patients with diabetes, 4) quantify time burden and number of episodes of hypoglycemia, 4) study hyperglycemic burden and 5) analyze glucose variability. The research staff will explain the study to patients that meet all inclusion criteria. Patients will get time to understand the study, review the consent document, ask questions to the PI, and then provide their consent to participate in the study. On Day 1 of the study, a CGM (Freestyle Libre) device will be placed on patients with CKD 3b-5 which will be worn for 14 consecutive days. Patients will return on Day 14 to remove the CGM device. HbA1c and fructosamine values will be drawn on Day 14 and these results will be compared with average glucose monitoring values as recorded on the CGM device. Incidence, duration, and severity of both hypoglycemic and hyperglycemic events will be analyzed. It is our hypothesis that there will be significant variability in the serum HbA1c values when compared with calculated HbA1c from CGM readings. We also hypothesize that the results will reflect a greater incidence of hypoglycemia in this population by CGM analysis.

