4. OBJECTIVE(S)/SPECIFIC AIMS AND HYPOTHESES

- *A concise statement of the goal(s) of the current study.*
- *The rationale for and specific objectives of the study.*
- *The goals and the hypothesis to be tested should be stated.*

- The goals of our study is to 1) determine accuracy of HbA1c and serum fructosamine testing as measures of glucose control, 2) better understand test characteristics in the late stage CKD population (correlation, linear equation, slope, Y intercept, average glucose at different HbA1c levels), 3) develop a preliminary understanding of how

test characteristics differ in late stage CKD compared to other patients with diabetes, 4) quantify time burden and number of episodes of hypoglycemia, 5) study hyperglycemic burden and 6) analyze glucose variability.

- It is our hypothesis that there will be significant variability in the serum HbA1c values when compared with calculated HbA1c from CGM readings. It is our hypothesis than the incidence of hypoglycemia will be high in patients with CKD 3b-5.

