10. ENDPOINTS

- *Describe the primary and secondary study endpoints*
- *Describe any primary or secondary safety endpoints*

- Primary End-Points: 1) Correlation between HbA1c and mean glucose concentration measured by CGM; 2) Characterization of hypoglycemic events, number, severity and duration. (Also, a safety end-point).
- Secondary End-Points: 1) Correlation between serum fructosamine and mean glucose concentration measured by CGM, 2) Determination of HbA1c and serum fructosamine regression equation, slope, Y intercept, average glucose at different test levels, 3) Number of hyperglycemic events and duration of each hyperglycemic event, 4) Study glucose variability as measured by mean amplitude of glucose excursion

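### The slope and intercept named as test characteristics come from regressing AMG on the marker, so marker scatter alone changes them and could be misread as bias

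*Combined protocol and SAP*

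**What the plan says.** Section 12 states that "A simple linear regression model will be applied to estimate the relationship between AMG and HbA1c". That sentence leaves the direction open, but the next one settles it: "prediction of mean AMG together with 95% confidence intervals will be calculated at different levels of HbA1c". AMG is the outcome and HbA1c the predictor. Later in the section, "If a linear relationship is established then slope, Y-intercept and correlation coefficient will be calculated". Fructosamine gets the same analysis, and subgroup slopes and intercepts are to be compared with those of the overall line.

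Section 4 sets as a goal to "better understand test characteristics in the late stage CKD population (correlation, linear equation, slope, Y intercept, average glucose at different HbA1c levels". Section 10 makes the regression equation, slope and intercept a secondary endpoint. Sections 2 and 4 also aim to "develop a preliminary understanding of how test characteristics differ in late stage CKD compared to other patients with diabetes", but no comparator equation or method is given. The hypothesis in section 4 is that "there will be significant variability in the serum HbA1c values when compared with calculated HbA1c from CGM readings". Section 12 contains no analysis of that variability: no regression of the marker on AMG, no paired difference, no residual SD and no errors-in-variables method.

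**The concern.** If HbA1c scatters around the value that glucose would predict, that scatter is error in the predictor of the planned model. It pulls the slope toward zero and, for a positive slope and a positive mean HbA1c, raises the intercept. No systematic bias is needed. Scatter of this kind is one reading of what section 4 hypothesizes.

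The size of the effect also depends on how widely glucose varies in the cohort. Two populations, or two subgroups, in which HbA1c responds to glucose identically can therefore yield different planned lines. This matters for the goal of describing how the test behaves in late-stage CKD and for the comparison with other patients. A marker that is noisier in CKD and a marker that responds differently to glucose in CKD are different findings, and the planned slope and intercept mix them.

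**Working it through.** The documents give no expected slope, intercept, correlation, SD or scatter, so there is no figure of the plan's to reproduce. From the documents: 80 subjects (sections 7 and 8), at least 7 days of CGM (section 12) and 14 days intended (section 11). Everything else here is assumed: HbA1c unbiased at b = 30 mg/dL per 1%, mean HbA1c 7.5%, mean AMG 165 mg/dL (true intercept 165 - 30 × 7.5 = -60), AMG SD 45 mg/dL.

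**Formulas.** Let X be the glucose-determined part of HbA1c, with SD 45/30 = 1.5, and s the SD of the extra scatter.
- λ = Var(X) / (Var(X) + s²)
- expected planned slope = λb
- expected planned intercept = 165 - λb × 7.5

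| s | λ | Slope (true 30) | Intercept (true -60) |
|---|---|---|---|
| 0.3 | 2.25/2.34 = 0.962 | 28.8 | -51 |
| 0.5 | 2.25/2.50 = 0.900 | 27.0 | -38 |
| 0.8 | 2.25/2.89 = 0.779 | 23.4 | -10 |
| 1.0 | 2.25/3.25 = 0.692 | 20.8 | +9 |

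A simulation at n = 80 gives the same averages.

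**Dependence on the cohort.** With s = 0.5 and AMG SD 30 instead of 45, Var(X) = 1.0, λ = 1/1.25 = 0.80 and the slope is 24.0 rather than 27.0, with the same test and the same scatter.

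**What the distortion looks like.** The line turns about the cohort mean. At HbA1c 7.5% the fitted AMG is 165 for every s. A uniform shift of -0.5% in HbA1c behaves differently: the slope stays at 30, the intercept rises by 0.5 × 30 = 15 to -45, and AMG lies 15 mg/dL above the reference line at the observed mean HbA1c. So scatter imitates a proportional bias. At s = 0.8 a slope of 23.4 is also what a scatter-free HbA1c would give if it responded 1/0.779 = 1.28 times as steeply to glucose.

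**Marker on AMG.** If AMG has no error, regressing HbA1c on AMG has expected slope 1/30 = 0.0333 and intercept 7.5 - 165/30 = 2.0 at every s, and its residual SD estimates s. If AMG has error SD e, the slope is multiplied by 45²/(45² + e²):
- e = 7: 2025/2074 = 0.976
- e = 12: 2025/2169 = 0.934

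The residual variance becomes s² + 2.25 × (1 - that factor). For s = 0.3 and e = 12 this is 0.09 + 0.149 = 0.239, an SD of 0.49 rather than 0.30.

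**How often the 95% CI excludes the true slope** (simulated, n = 80, no correction):

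| s | Planned fit, e = 0 | Planned fit, e = 12 | Marker on AMG, e = 0 | Marker on AMG, e = 12 |
|---|---|---|---|---|
| 0.3 | 42% | 18% | 5% | 45% |
| 0.5 | 83% | 60% | 5% | 30% |
| 0.8 | 99.5% | 98% | 5% | 17% |
| 1.0 | 100% | 99.9% | 5% | 14% |

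**The case against.** Five points can be made for the plan.

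1. *The planned direction is right for part of the task.* Average glucose at a given HbA1c is a conditional mean, and regressing AMG on HbA1c estimates it without bias for this cohort. A reader might infer that predictions at, say, HbA1c 10% are wrong because they lie below the 240 mg/dL of the true line. They are not: at s = 0.8 the mean AMG of patients with HbA1c 10% is 165 + 23.4 × 2.5 = 223 mg/dL, and the planned fit returns that. This stands in full.
2. *Nothing says the parameters will be read as bias.* A reader might infer that scatter will be reported as a systematic shift. The documents contain no reading rule and promise only a preliminary comparison, so only the risk of misreading is supported. A uniform shift also has a different signature, so the confusion is with proportional bias, or with a shift if the intercept is read alone.
3. *The primary endpoint is untouched.* "Correlation between HbA1c and mean glucose concentration measured by CGM" is the same in either direction. It falls with scatter and not with a uniform shift: with AMG residual SD 15 and SD(X) 1.2, scatter of 0.7 takes r from 0.92 to 0.80. This stands, but r also depends on the cohort's glucose spread, so the signal is partial.
4. *Reversing the regression is not a cure.* AMG from 7 to 14 days carries error too. With scatter 0.3 and AMG error 12, the uncorrected reverse fit does worse than the planned one (45% against 18%). This stands, and it is why the fix includes a correction.
5. *The hypothesized variability has no stated size* and could mean systematic deviation rather than scatter. This stands, so the effect can only be shown as a range.

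**Conclusion.** The point holds for one use of the planned fit: reading its slope and intercept as properties of the test, or comparing them between subgroups or with other patients with diabetes. For that use they combine the marker's response to glucose, its scatter and the cohort's glucose spread. Under the stated assumptions, scatter SD of 0.3 to 1.0 moves the slope from 30 to between 28.8 and 20.8, and the intercept from -60 to between -51 and +9, with no bias present. The mechanism is the same for fructosamine, for which no size is computed here.

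The point does not reach the primary correlation endpoint or the table of average glucose by HbA1c level. A separate gap is that section 12 has no direct estimate of the variability in section 4's hypothesis. The change is worth making because it is cheap and answers that hypothesis. The primary analysis is not invalid.

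**What to change.** In section 12:

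- Keep the regression of AMG on each marker for average glucose at given marker levels, labelled as prediction for this cohort.
- Add a regression of each marker on AMG. Report the slope, the fitted marker value at fixed AMG levels and the residual SD in marker units. Correct the slope for AMG sampling error, estimated from each patient's daily CGM means, and note that AMG error also inflates the residual SD.
- State what the correction leaves in place: sensor bias that is constant within a patient, and the mismatch between a 7-14 day CGM window and the longer period that HbA1c reflects.
- For the section 4 hypothesis, report the paired difference between measured and CGM-calculated HbA1c, with the mean for bias and the SD for scatter. Name the conversion equation in advance.

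The cost is one more regression per marker and one paired summary on data already collected, plus a paragraph of text. The downside is two equations per marker, which must be labelled clearly so that neither is used for the other's purpose.

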7. ELIGIBILITY CRITERIA

- *Describe the characteristics of the subject population, including their anticipated number, age, ranges, sex, ethnic background, and health status. Identify the criteria for inclusion or exclusion of any subpopulation.*
- *Explain the rationale for the involvement of special classes of subjects, such as fetuses, pregnant women, children, prisoners or other institutionalized individuals, or others who are likely to be vulnerable. You cannot include these populations in your research, unless you indicate such in the protocol*
- *Similarly, detail exclusionary criteria: age limits, special populations (minors, pregnant women, decisionally impaired), use of concomitant medications, subjects with other diseases, severity of illness, etc.*

- We anticipate recruiting 80 subjects for this study. We anticipate a fair distribution of males and females, Caucasians, African Americans, and people from other ethnic groups. We anticipate that most patients in this age group are relatively healthy with possibly 1-5 past medical health problems.
- Inclusion Criteria: patients who are 18 years and older with the ability to speak and understand English and with T2DM AND CKD stages 3b-5. Vulnerable populations would include elderly and minorities, as listed in section 26 below for vulnerable populations. There are minimal risks of participating in this study for all subjects including vulnerable populations.
- Exclusion criteria: patients with Type I DM, ESRD on HD, hemoglobinopathies, who have received red blood cell transfusions in the last 12 weeks, with hemoglobin <9, current use of acetaminophen on a daily basis, steroid treatment in the prior 12 weeks, greater than 50% change in diabetes medications or new diabetes medications started in the prior 12 weeks, patients who are currently pregnant.

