8. NUMBER OF SUBJECTS

- *Indicate the total number of subjects to be accrued locally. If applicable, distinguish between the number of subjects who are expected to be pre-screened, enrolled (consent obtained), randomized and complete the research procedures.*
- *If your study includes different cohorts, include the total number of subjects in each cohort.*
- *If this is multisite study, include total number of subjects across all sites.*

There is an expected number of 80 recruited subjects from all aforementioned sites (Northwell Health Division of Nephrology, Division of Endocrinology, and Winthrop University Hospital Division of Nephrology).
We expect all patients will complete the research procedures

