16. WITHDRAWAL OF SUBJECTS

- *Describe anticipated circumstances under which subjects will be withdrawn from the research without their consent*
- *Describe procedures for orderly termination*
- *Describe procedures that will be followed when subjects withdraw from the research, including partial withdrawal from procedures with continued data collection.*

During the monitoring phase, the diabetes medications will not be changed unless indicated by their private endocrinologist or internist, in which case the patient will be withdrawn from the study for fulfilling an exclusion criterion. Furthermore, patients with less than 7 days of CGM measurements will be excluded from statistical analysis due to limited data collection.
--

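### Subgroup slopes are compared with the all-patient fit that contains them, which dilutes any difference due to a factor, and no between-subgroup difference with a confidence interval is planned

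*Combined protocol and SAP*

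**What the plan says.** Section 12 (Statistical Analysis) defines one simple linear regression relating AMG to HbA1c. It names no subset, so the fit covers every analysed patient. The section then goes on as follows:

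- Precision is planned for one output: "prediction of mean AMG together with 95% confidence intervals will be calculated at different levels of HbA1c".
- Factors are introduced with "Influence of factors such as age, gender on the relationship between HbA1c and AMG will be examined through a multivariate regression model". No product term is written down.
- The next sentence gives the comparison: "Slopes and intercepts of the regression equations for the individual subgroups will be compared to those of the simple linear regression model". No test, no subgroup-versus-subgroup difference and no CI is named. Subgroups are not defined, and no age cut is given.
- A quadratic model is foreseen if the relationship is not linear.
- For the second marker, "The same analysis will be performed to establish the relationship between AMG and serum fructosamine".

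Section 10 (Endpoints) lists the related secondary endpoint as "Determination of HbA1c and serum fructosamine regression equation, slope, Y intercept, average glucose at different test levels". On numbers, section 8 says "There is an expected number of 80 recruited subjects from all aforementioned sites", and section 16 adds that "patients with less than 7 days of CGM measurements will be excluded from statistical analysis due to limited data collection". Subgroup sizes are not given. Section 7 says only "We anticipate a fair distribution of males and females, Caucasians, African Americans, and people from other ethnic groups".

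**The concern.** If the question is whether a factor changes the relationship, the natural quantity is the slope in one subgroup minus the slope in the other. Section 12 instead measures each subgroup against a fit that already includes it. Part of the subgroup's own slope is therefore subtracted from itself, and the larger the subgroup, the more is lost. The same underlying difference gives a different number depending on which subgroup is named, and contrasts for different factors cannot be set side by side unless their splits match.

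A reader also gets no interval for the difference. With at most 80 patients, fewer after the 7-day rule, a small contrast may mean that the relationship is alike across subgroups or only that the study cannot tell. The plan as written does not separate the two.

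**Working it through.** The plan gives no subgroup size, SD, slope or precision target for this comparison, so there is no figure of its own to reproduce. From the documents: N = 80 (section 8). Assumed: the subgroup splits, the slope differences, the HbA1c distributions and the values of r. Unless stated otherwise, slopes are in residual SD of AMG per SD of HbA1c.

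1. **Part against whole.** With similar HbA1c distributions in subgroups A and B and no level shift, the all-patient slope is b_all = f·b_A + (1 − f)·b_B, where f is A's share. Hence b_A − b_all = (1 − f)(b_A − b_B).
   - 40/40: 1 − 40/80 = 50% shown.
   - 24/56: 1 − 24/80 = 70% if the smaller subgroup is named; 1 − 56/80 = 30% if the larger is named.

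2. **Simulation, 20,000 runs per case.**
   - 40/40, true difference 0.626: expected 0.5 × 0.626 = 0.313; simulated contrast 0.312.
   - 24/56, true difference 0.684: expected 0.7 × 0.684 = 0.479 and 0.3 × 0.684 = 0.205; simulated 0.480 and 0.206.

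3. **Check in clinical units.** Assume a slope of 28 mg/dL per 1% HbA1c, residual SD 25 mg/dL, HbA1c SD 1.3 and a true slope difference of 10 (8,000 runs). The planned contrast averages 7.51, 5.01 and 2.50 for subgroups of 20, 40 and 60 out of 80. The HbA1c×factor interaction averages 10.01, 9.99 and 9.96.

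4. **If the subgroups also differ in mean HbA1c (by D) and in level (by L), 40/40.**
   - True difference 0.626, D = 0.3 and L = ±0.3: contrast 0.291 to 0.337, or 47–54% shown. D = 0.5 and L = ±0.5: 0.254 to 0.373, or 41–60%.
   - Equal true slopes: the size of the contrast is L·f(1 − f)·D / (1 + f(1 − f)D²). For D = L = 1 this is 0.25/1.25 = 0.20. For 0.5 it is 0.0625/1.0625 = 0.06. For 0.3 it is 0.0225/1.0225 = 0.02.

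5. **What an interaction model would deliver at N = 80.** The mean 95% CI half-width for the slope difference is 0.46 (40/40) and 0.51 (24/56), with simulated coverage 94.8–95.3%. The overall slope in these units is r/√(1 − r²): 1.333, 0.980 and 0.577 for r = 0.8, 0.7 and 0.5. The half-width is then 35–38%, 47–52% and 80–88% of the overall slope. At an assumed 30/30 analysed it is about 0.53 to 0.55.

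6. **Why centre HbA1c.** At 40/40 the level difference at mean HbA1c has half-width t·√(1/40 + 1/40) = 0.445 residual SD. The intercept difference at HbA1c = 0, outside the data, has half-width 2.15 (assumed HbA1c mean/SD 7/1.5) to 3.64 (8/1.0).

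**The case against.** **The contrast may answer another question.** If the aim is to see whether the overall equation holds in a given subgroup, subgroup minus overall is the right quantity, and no endpoint or hypothesis asks for a gender or age difference in slope. This stands as a limit: the contrast has the wrong size only when the target is the between-subgroup difference. But section 12's own preceding sentence frames the question as the influence of factors on the relationship, and for that the part-against-whole comparison is a poor answer.

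**The multivariate model may already contain the interaction.** It could; influence on a relationship is effect-modification language. But no product term is stated. A main-effects model would shift only the level and estimate no slope difference.

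**Readers can subtract the subgroup equations.** True for the point estimate. No standard errors or intervals are planned for those equations, so the precision of the difference would remain unknown.

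**Stronger readings that the documents do not support.** A reader might infer that the comparison has a distorted type I error or loses power. The plan names no test, so there is no error rate to criticise. With the overlap handled correctly, the contrast carries almost the same information as the interaction: their correlation is 0.98 at 40/40 and 0.99 at 24/56. A reader might also infer that spurious subgroup differences are likely. For modest shifts the false contrast is 0.02 to 0.06, at most about 13% of the interaction half-width (0.06/0.46).

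**Conclusion.** The point holds as a modest one. The stated comparison is poorly matched to the question that section 12 sets. As a measure of how a factor changes the slope, it shows about 50% of the between-subgroup difference at an assumed 40/40 split, and 70% or 30% at an assumed 24/56 split. These shares rest on similar HbA1c distributions and no level shift. With shifts of up to 0.5 SD in both, the 50% becomes 41–60%. No between-subgroup difference with a CI is planned, for HbA1c or for fructosamine.

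It would be too much to infer that the main results are compromised. The analysis is exploratory and supports a secondary endpoint. The overall slope and Y intercept are still reported, and the primary correlation between HbA1c and mean glucose does not depend on it.

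**What to change.** Replace the comparison sentence in section 12 with the following.

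- For each named factor, the multivariate model is AMG ~ centred HbA1c + factor + HbA1c×factor, with gender categorical and age continuous.
- Report the slope difference, and the level difference at the centring value, with 95% CIs, labelled exploratory. For age, these are changes per stated number of years.
- Do the same with fructosamine in place of HbA1c.
- Keep the overall equation. Keep subgroup equations as descriptive output for categorical factors only. For age, show model-based equations at stated ages.
- If the quadratic model is used, report factor differences in predicted AMG at stated HbA1c levels, from a model that includes the products of the factor with the HbA1c terms.

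This is a wording change and needs no new data. The cost is a few more exploratory estimates that will be imprecise, more so after the 7-day CGM exclusion, and they should be presented as such.

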3. INTRODUCTION/BACKGROUND MATERIAL/PRELIMINARY STUDIES AND SIGNIFICANCE

- *Describe and provide the results of previous work by yourself or others, including animal studies, laboratory studies, pilot studies, pre-clinical and/or clinical studies involving the compound or device to be studied.*
- *Include information as to why you are conducting the study and how the study differs from what has been previously researched, including what the knowledge gaps are.*
- *Describe the importance of the knowledge expected to result*

- Studies evaluating the accuracy of HbA1c and fructosamine values in patients with T2DM and CKD 3b-5 is scarce. A pilot study by Konya, Nq, Cox, et al., evaluated the accuracy of HbA1c in 15 T2DM patients with CKD3-4 receiving iron or erythropoiesis and concluded that other glycemic markers such as fructosamine or glycated albumin maybe valuable markers in assessing glycemic control in this patient population. Another pilot study by Vos, Schollum, et al., evaluated HbA1c, glycated albumin, and fructosamine in 25 patients with CKD 4-5 matched with T2DM patients with no renal dysfunction. These patients wore a CGM device for only 48 hours. The results of this study indicated that glycated albumin was a better marker than fructosamine and HbA1c in patients with CKD 4-5.
- This investigation is an attempt to add to the current available literature by assessing the accuracy of HbA1c and evaluating if fructosamine and/or CGM data are better tools for short term and long-term diabetes management in patients with CKD 3b-5 (not on hemodialysis (HD)) specifically. Our aim is also to assess the incidence of hypoglycemic and hyperglycemic excursion in these patients by CGM analysis.
- This study allows us to understand which marker (HbA1c, fructosamine, CGM data) is most reliable for diabetes management in patients with CKD 3b-5. Hypoglycemia in this specific subset of patients poses significant risks to increase morbidity and mortality. Improvement in such knowledge of glycemic control will lead to decreased morbidity and mortality in this population.

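### Section 3 promises to say which glycaemic marker is best, but section 12 never estimates the difference between HbA1c and fructosamine

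*Combined protocol and SAP*

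**What the plan says.** Section 3 states the comparative intent twice. It describes the investigation as "evaluating if fructosamine and/or CGM data are better tools for short term and long-term diabetes management" and then says: "This study allows us to understand which marker (HbA1c, fructosamine, CGM data) is most reliable for diabetes management in patients with CKD 3b-5".

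The formal sections are narrower. The first goal in section 4 is to "determine accuracy of HbA1c and serum fructosamine testing as measures of glucose control", and neither hypothesis there ranks the tests. Section 10 lists two separate endpoints: "Correlation between HbA1c and mean glucose concentration measured by CGM" (primary) and "Correlation between serum fructosamine and mean glucose concentration measured by CGM" (secondary).

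Section 12 follows section 10. For HbA1c: "A simple linear regression model will be applied to estimate the relationship between AMG and HbA1c". For fructosamine: "The same analysis will be performed to establish the relationship between AMG and serum fructosamine". The summaries are per marker: "If a linear relationship is established then slope, Y-intercept and correlation coefficient will be calculated". The only confidence intervals planned are for predicted mean AMG at given marker levels. The only regressions to be compared are subgroup fits against the overall fit. Section 11 has both blood tests drawn on Day 14 from the same patients.

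**The concern.** A reader of the results will use section 3's question: is fructosamine better than HbA1c in this population? The plan delivers two coefficients and nothing on how far apart they could be by chance. Two sample correlations are almost never equal, so one marker will always look better.

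The two correlations share the same patients and the same AMG, so they are dependent. The uncertainty of their difference cannot be recovered from the two regressions alone, because it also depends on how strongly the markers correlate with each other, and the plan does not report that. At stake is a claim that one marker is superior when none is, or a real difference left unquantified although the paired data could address it.

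**Working it through.** **Inputs from the protocol.** Recruitment target 80, with all expected to complete (section 8). Patients with under 7 days of CGM are left out (section 12). Patients whose diabetes medication is changed during monitoring are withdrawn (section 16). The protocol gives no expected correlation, alpha, power or sample size formula, so there is no stated figure to reproduce.

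**Assumptions.** AMG, HbA1c and fructosamine jointly normal; each marker's true correlation with AMG 0.5 to 0.8; correlation between the markers 0.4 to 0.8; two-sided 5% level.

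**Step 1: chance gap when the markers are equally good.** Let both markers correlate ρ with AMG and κ with each other. The large-sample variance of the difference between the two sample correlations is

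Var = (2/n) × [(1 − ρ²)² − c], with c = κ(1 − 2ρ²) − ½ρ²(1 − 2ρ² − κ²).

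With ρ = κ = 0.6 and n = 80:
- (1 − 0.36)² = 0.4096
- c = 0.6 × 0.28 − 0.18 × (−0.08) = 0.168 + 0.0144 = 0.1824
- Var = 2 × 0.2272 / 80 = 0.00568, so SD = 0.075
- a gap of 0.10 is 0.10 / 0.0754 = 1.33 SD, exceeded in either direction with probability about 0.19

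Simulation (20,000 studies per row, n = 80) agrees:

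| True r with AMG (both) | Marker–marker r | SD of gap | Gap over 0.05 | Gap over 0.10 |
|---|---|---|---|---|
| 0.5 | 0.4 | 0.103 | 63% | 33% |
| 0.6 | 0.5 | 0.085 | 56% | 24% |
| 0.6 | 0.6 | 0.076 | 51% | 19% |
| 0.6 | 0.7 | 0.067 | 45% | 13% |
| 0.7 | 0.5 | 0.071 | 47% | 16% |
| 0.7 | 0.6 | 0.065 | 44% | 12% |
| 0.7 | 0.7 | 0.059 | 39% | 9% |
| 0.8 | 0.8 | 0.040 | 20% | 1% |

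The 9% to 19% range is for all correlations between 0.6 and 0.7. Over the whole assumed grid the range is 1% to 33%.

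**Step 2: fewer analysable patients.** With all correlations 0.6, a chance gap over 0.10 occurs in 19% of studies at n = 80, 22% at n = 70 and 25% at n = 60. The smaller numbers are illustrations, since the protocol predicts no losses.

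**Step 3: what a paired comparison would deliver.** Williams' test for two correlations sharing a variable kept the false-positive rate at about 5% (4.7% to 5.3% at n = 80). Its power at n = 80:

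| True r with AMG | Power, marker–marker r = 0.6 | Range, marker–marker r 0.5 to 0.7 |
|---|---|---|
| 0.70 vs 0.60 | 29% | 25% to 36% |
| 0.75 vs 0.60 | 61% | 53% to 72% |
| 0.70 vs 0.50 | 77% | 68% to 87% |
| 0.80 vs 0.60 | 89% | 84% to 95% |

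For 0.70 versus 0.60 with markers correlated 0.6, 80% power needs about 300 patients. In that setting the sample puts the markers in the wrong order in 5% to 10% of studies (marker–marker r 0.5 to 0.7).

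**Step 4: is residual SD a second piece of evidence?** For linear fits in the same patients, residual SD = SD(AMG) × √[(1 − r²)(n − 1)/(n − 2)]. SD(AMG) and n are common to both fits, so this ranks the markers exactly as |r| does. It supplies a glucose scale but no separate test.

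**The case against.** The best defence is scope. Ranking language appears only in the background. The goals in section 4 and the endpoints in section 10 treat each test on its own, and section 12 matches them. On that view the plan is coherent and section 3 is merely loosely worded. This stands in part: a reader might infer that the head-to-head comparison is a stated objective or endpoint that the analysis fails to deliver, and the documents do not support that. But section 3 does more than set the scene. It says what the investigation is evaluating and what it will let readers conclude, and nothing in the plan can carry that conclusion.

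A reader might also infer that the sponsor intends to rank the markers by eye, by overlap of confidence intervals, or by treating the correlations as independent. Section 12 states none of these, and it plans no interval for a correlation at all. The gap is an absent comparison, not an invalid one.

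One sentence in section 12 names AMG, HbA1c and fructosamine together and could be taken for a joint model. The text around it describes separate fits, and no contrast between markers is specified on either reading.

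Finally, the chance gap is small if all correlations are high, and a paired comparison at n = 80 is weak for modest differences. Both points stand. They are reasons to report an interval and accept an inconclusive answer, not reasons to leave the difference without one.

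**Conclusion.** The concern holds in a limited form: section 3 announces a conclusion about relative reliability that section 12 does not estimate. No endpoint analysis is invalidated.

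At n = 80, a chance gap over 0.10 between equally good markers is a realistic possibility under moderate correlations and a remote one if all correlations are near 0.8. Which applies cannot be known from the documents, because every correlation used here is an assumption. Joint normality is assumed as well.

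Section 3 also lists CGM data among the markers to be ranked. CGM mean glucose is the reference in both regressions, so neither the present plan nor an added comparison of the two blood tests can rank it.

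**What to change.** Add to section 12 one comparison, labelled exploratory, in patients with both blood tests and at least 7 days of CGM:

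- Estimate r(HbA1c, AMG) − r(fructosamine, AMG) with a 95% confidence interval from a bootstrap that resamples patients. Williams' test is an alternative. Name one in advance as governing. The power figures above are for Williams' test; the bootstrap interval was not simulated.
- Call a marker better only if the interval for the difference in r excludes zero. Otherwise report that no difference was shown, and say that this does not mean the markers are equivalent.
- Give the residual SD of AMG for each marker in mg/dL as description only.
- State the limited power: about 29% for 0.70 versus 0.60 and about 61% for 0.75 versus 0.60, with the markers correlated 0.6.

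Reword section 3 to match, and take CGM data out of the ranking. If the sponsor does not want the comparison, removing the claim about the most reliable or better marker from section 3 would also resolve the mismatch, but the study would then leave that question unanswered.

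The cost is a few lines of text and one calculation on data already being collected, with no added patients, visits or tests. The drawback is that the comparison may well be inconclusive.
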